3.2 Trial Plan

An overview of assessments and study vaccinations is provided in Table 3.1 Study procedures.

Each potential subject will sign and date the ICF. In addition to the Screening Visit, all included subjects will attend 8 study visits, will receive 4 follow-up phone calls, and will be contacted 6 months after the last vaccination for a safety follow-up.

Vaccination

All subjects will receive 3 injections of either CYD dengue vaccine or placebo at Day (D) 0, Month (M) 6, and M12.

Blood sampling

A number of immunological (hepatitis B virus antigen [HBsAg], hepatitis C virus [HCV] Abs), hematological (hemoglobin, hematocrit, platelet count, white blood cells count), and biochemical (aspartate aminotransferase [AST], alanine aminotransferase [ALT], urea and creatinine) parameters will be assessed at screening (unless the tests have already been performed as part of routine follow-up within the 4-week time window). The subject's dengue serostatus will be determined by RDT or ELISA during the Screening Visit.

Dengue, YF, and Zika baseline status will be assessed at D0.

Dengue vaccinal viremia will be assessed at D7 and D14 post-Inj 1.

Dengue neutralizing antibody (Ab) levels will be assessed at baseline (V01; prior to Inj 1) and 28 days after each injection.

If no HIV viral load and CD4 count results are available prior to each injection (ie, tests have not been performed within 2 months before injection visit), tests will be performed to ensure that results are available at the time of injection visit.

HIV viral load and CD4 count will be assessed 28 days after each injection. In case an increase in HIV viral load (plasma HIV-1 RNA > 1000 copies/mL 28 days post-injection after having been undetectable [< 50 copies/mL] pre-injection) or a decrease in CD4 count (decrease greater than 30% 28 days post-injection compared to the pre-injection value) is observed, a second blood sample is to be taken 4 weeks later for confirmation, as it is current local practice to confirm abnormal and significant deterioration of HIV-condition related results (20).

Collection of safety data

Safety data will be collected following each injection. Clinical site personnel will record immediate AEs that occur within the 30 minutes after injection. Subjects will record in the diary card (DC) information about solicited injection site reactions from D0 to D7 post-injection, about solicited systemic reactions from D0 to D14 post-injection, and unsolicited AEs occurring up to 28 days post-injection. Information on serious adverse events (SAEs) will be reported throughout the study. Serious and non-serious adverse events of special interest (AESIs) will be collected in defined time windows according to the type of AESI.

DCs will be provided to subjects to collect information on SAEs in-between injections (ie, from 28 days to 6 months post-Inj 1; and from 28 days to 6 months post-Inj 2). A memory aid (MA) will be provided to subjects to help them record SAEs during the 6 months safety follow-up (from

28 days post-Inj 3 to 6 months after last injection). Subjects are to contact the Investigator (within the first 5 days after fever onset) in case of hospitalization for suspected dengue disease at any time during the study for virological confirmation of the disease.

Clinical site personnel will review the safety data with the subjects during post-injection visits.

Table 3.1: Table of Study Procedures

Phase II Trial: a Screening Visit (Scr.), 8 Visits (V), and 5 Phone Calls (PC); 3 Injections; 7 to 9 Blood Samples; 18-month duration per subject

Visit (V) and Phone Call (PC) Number	Scr.*	V01*	V02	V03	V04	V05	PC1	PC2	V06	V07	PC3	PC4	V08	6-month Follow-up†
Trial Timelines Injection (Inj); Day (D); Month (M)	-D28 to – D0	Inj 1 (D0)	Inj 1 +7D	Inj 1 +14D	Inj 1 +28D	Inj 2 (M6)	Inj 2 +7D	Inj 2 +14D	Inj 2 +28D	Inj 3 (M12)	Inj 3 +7D	Inj 3 +14D	Inj 3 +28D	Last Inj +6 months
Time Windows (Days)			+3	+3	+14	±20	+3	+3	+14	±20	+3	+3	+14	+30
Phone calls							X†	X†			X†	X†		X†
Informed Consent	X													
Inclusion/Exclusion Criteria	X	X												
Demography/Body Stature		X												
Significant Medical History	X	X												
History of dengue infection/vaccination, YF vaccination, or Zika	X	X												
Physical/Clinical Examinations‡	X	X					X	†	†		X	†	†	†
Temperature§		X					X				X			
IRT Contact	X	X					X				X			
Randomization		X												
Concomitant Therapy**		X	X	X	X	X			X	X			X	
Urine Pregnancy Test††		X					X				X			
Contraindications							X				X			
Blood Sampling														
Screening tests‡‡	X													
Previous exposure to dengue using RDT or dengue ELISA §§	X													
FV status (dengue, YF, and Zika)***		BL1												
Dengue neutralizing Abs***		BL1				BL4				BL5				BL6
Dengue vaccinal viremia			BL2	BL3										
CD4 count and HIV Viral Load†††		†††			BL4†††	†††			BL5†††	†††			BL6†††	

Visit (V) and Phone Call (PC) Number	Scr.*	V01*	V02	V03	V04	V05	PC1	PC2	V06	V07	PC3	PC4	V08	6-month Follow-up†	
Trial Timelines Injection (Inj); Day (D); Month (M)	-D28 to – D0	Inj 1 (D0)	Inj 1 +7D	Inj 1 +14D	Inj 1 +28D	Inj 2 (M6)	Inj 2 +7D	Inj 2 +14D	Inj 2 +28D	Inj 3 (M12)	Inj 3 +7D	Inj 3 +14D	Inj 3 +28D	Last Inj +6 months	
Time Windows (Days)			+3	+3	+14	±20	+3	+3	+14	±20	+3	+3	+14	+30	
Virological confirmation of dengue by NS1 Ag ELISA and/or WT dengue RT-PCR	All acute febrile illness with diagnosis of dengue requiring hospitalization within the first 5 days after fever onset, occurring after the first visit (V01) and until the end of the 6-month safety follow-up														
Injection		Inj. 1				Inj 2				Inj 3					
30-Min. Observation Period – Collection of immediate events		X				X				X					
Injection Site Reactions & Systemic Events Assessment	Solicited injection site reactions will be collected for Days 0–7 after each injection. Solicited systemic reactions will be collected for Days 0–14 after each injection. Unsolicited events will be collected for Days 0–28 after each injection.														
Diary Card (DC)\$\$\$\$		DC1	DC1	DC1	DC2 DC1 DC1	DC3 DC2 DC2			DC4 DC3 DC3	DC5 DC4 DC4			DC5 DC5		
Memory Aid (MA)\$\$\$\$													MA		
Termination Record****													X		
SAEs and Serious AESIs††††	####	SAEs from the first visit (V01) and until the end of the 6-month safety follow-up; AESIs in defined time windows according to the type of AESI													

* Serology, hematology and biochemistry results, as well as all other information collected as part of the screening of potential subjects will be captured in the source document. Inclusion/exclusion criteria, significant medical history, history of dengue infection/vaccination, of YF infection/vaccination, and of Zika infection, physical/clinical examinations, CD4 count and HIV viral load results will be captured in the CRF at V01 for eligible subjects. The Screening Visit and Visit 1 can be simultaneous for subjects tested positive by RDT and whose tests have been performed in appropriate time windows (within 4 weeks before injection for hepatitis serology, hematology, and biochemistry; within 2 months for CD4 count and HIV viral load) as part of the subject's routine follow-up.

† A follow-up visit can be arranged depending on the information provided during the phone call, at the Investigator's discretion. In the case of the 6-month follow-up phone call, this can be anticipated to perform the 6 months follow up after the last vaccination in case of early termination.

‡ A full physical/clinical examination will be conducted on each vaccination visit (before vaccine injection), and at the Investigator's discretion if at the time of other visits, based on the health status of the subject for the other visits.

§ Subject's temperature is to be measured before each injection, and at the Investigator's discretion at the time of other visits, if necessary based on the health status of the subject for the other visits. Temperatures will be recorded in source document only.

- ** Concomitant therapy will be collected for Days 7, 14 and 28 days post-Injection 1 as well as before and 28 days after Injection 2 and Injection 3.
- †† In all female subjects, result of urine pregnancy test should be confirmed as negative before each vaccine injection.
- ‡‡ Screening tests will be performed at local laboratory within 1 and 4 weeks before the first vaccination. These tests will include: serology (HBsAg, HCV Ab), hematology (hemoglobin, hematocrit, platelet count, white blood cells count), and biochemistry (AST, ALT, urea and creatinine). HBsAg and HCV tests will not be performed in case the information is already available in subject's medical history. If serology, hematology, and biochemistry results are available and were obtained within 4 weeks before first injection, tests do not need to be performed again.
- §§ Tests will be performed sequentially. RDT will be performed first, and IgG ELISA will only be performed on subjects who tested negative for RDT. Subjects who previously tested negative by RDT can be re-screened using dengue IgG ELISA.
- *** Blood sample to be collected before vaccine injection.
- ††† Pre-injection HIV viral load and CD4 count will come from routine periodical tests of subjects as per local guidelines. For subjects for whom CD4 count is not part of the routine periodical follow-up as per guidelines, the Investigator will assess CD4 count to ensure that results are available at the time of Visit 1. Likewise, if CD4 count is not available before Inj 2 and Inj 3 (for checking contraindication) the Investigator will assess CD4 count to ensure that results are available at the time of Inj 2 and Inj 3. Pre-injection CD4 count test should be performed within 2 months before the corresponding vaccination visit.
- †††† If an increase in HIV viral load (plasma HIV-1 RNA increase > 1000 copies/mL 28 days post-injection after having been undetectable [< 50 copies/mL] pre-injection) or a decrease in CD4 count (decrease in CD4 count greater than 30% assessed 28 days post-injection compared to pre-injection value), another blood sample is to be taken 4 weeks later for confirmation.
- §§§ DCs are used for the collection of solicited and unsolicited AEs and concomitant medication. DC2 and DC4 are used for the collection of medical events and/or hospitalization and medications at the time of the event in the period between V04 and V05 and V06 and V07, respectively. Each DC is to be reviewed and collected by the site at the following visit. The MA is used for the collection of medical events and/or hospitalization and medications at the time of the event for 6 months after the third injection. The caller will ascertain whether any SAEs occurred since the last contact. During the follow-up period, subjects will be instructed to contact the clinical site if they are hospitalized or experience an AE that might be considered serious.
- **** Termination record will be checked either during a planned study visit or a phone call.
- ††††† Serious AESIs will be reported after each injection in defined time windows as follows: serious hypersensitivity/allergic reactions occurring within 7 days, serious viscerotropic disease occurring within 30 days, serious neurotropic disease occurring within 30 days; hospitalized suspected dengue disease will be reported during the entire study. Non-serious AESIs (ie, hypersensitivity / allergic reactions) will be reported within 7 days after each injection.
- †††††† SAEs related to study procedures (from Screening Visit to V01) will be reported on paper form; at V01, all SAE information for eligible subjects reported on paper SAE form should be transcribed into the EDC system. From V01 until the end of the safety follow-up, all SAEs and AESIs in defined time windows according to the type of AESI will be documented in the EDC.

4 Endpoints and Assessment Methods

4.1 Primary Endpoints and Assessment Methods

See Section 9.1 of the protocol.

4.2 Secondary Endpoints and Assessment Methods

See Section 9.2 of the protocol.

4.3 Observational Endpoints and Assessment Methods

See Section 9.3 of the protocol.

4.4 Derived Endpoints: Calculation Methods

4.4.1 Safety

Terms used in the clinical safety tables to describe the safety events are specified below:

- AE: Adverse event; includes immediate, solicited, and unsolicited including non-serious and serious adverse events.
- AR: Adverse reaction; adverse reaction corresponds to a related AE.
- Immediate: Unsolicited systemic AE checked "immediate (within 30 minutes from the vaccination)" by the investigator in the case report form (CRF).
- Solicited reaction: Event pre-listed in the CRF, and which occurred during the solicited period (period is usually 0 to 7 days for injection site reactions and 0 to 14 days for systemic reactions post-vaccination).
- Unsolicited AE: AE recorded in the CRF as Immediate Unsolicited Systemic Events or Unsolicited Systemic Events or Unsolicited Injection Site Reactions.
- Unsolicited injection site reactions are always considered as related to the vaccine injection and analyzed as ARs.
- SAE: Unsolicited AE considered serious by the investigator.
- Hospitalized virologically-confirmed dengue case: Hospitalized suspected dengue disease is defined as an acute febrile illness with diagnosis of dengue requiring hospitalization (inpatient care). The confirmatory dengue diagnosis is performed through virological detection (eg, dengue non-structural protein 1[NS1], dengue reverse transcription-polymerase chain reaction [RT-PCR]).

4.4.1.1 **Solicited Reactions**

4.4.1.1.1 **Daily Intensity**

All daily records for solicited reactions will be derived into daily intensity according to the following classification: None, Grade 1, Grade 2, Grade 3, or Missing.

For the derivation of daily intensities the following sequential steps will be applied:

- 1) Solicited reactions (except Fever/Pyrexia) with an investigator presence recorded as “No” and with all daily records missing then all daily intensities will be derived as None.
- 2) For non-measurable solicited reactions, daily intensities will correspond to daily records reported in the clinical database. For measurable solicited reactions the daily measurements reported in the clinical database will be converted based upon the intensity scales defined in Section 9.1.1.3.2 of the protocol; this assumes a reaction that is too large to measure (non-measurable [NM]) is Grade 3.

Note: The maximum intensity on the ongoing period is derived from the record of the maximum intensity/measurement after the end of the solicited period following the rule described above.

4.4.1.1.2 **Maximum Intensity**

Maximum intensity is derived from the daily intensities computed as described in [Section 4.4.1.1.1](#) and is calculated as the maximum of the daily intensities over the period considered.

Note: The maximum intensity could be considered as “None” (ie, not a reaction) in the analysis despite being considered a reaction by the Investigator (eg, Injection site erythema measurement > 0 mm and < 25 mm).

4.4.1.1.3 **Presence**

Presence is derived from the maximum intensity on the period considered:

- None: No presence
- Grade 1, Grade 2, or Grade 3: Presence
- Missing: Missing presence

Subjects with at least one non-missing presence for a specific endpoint will be included in the analysis. Conversely, those without a non-missing presence will not be included in the analysis of the endpoint.

4.4.1.1.4 **Time of Onset**

Time of onset is derived from the daily intensities computed as described in [Section 4.4.1.1.1](#). It corresponds to the first day with intensity of Grade 1, Grade 2, or Grade 3.

Note: If a reaction is not continuous (ie, reaction occurs over two separate periods of time intervened by at least one daily intensity Missing or None) then the time of onset is the first day of the first occurrence.

Time of onset will be displayed by period as follows:

- Injection site reactions (D0-D7): D0-D3, D4-D7
- Systemic reactions (D0-D14): D0-D3, D4-D7, D8-D14

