5.3.1.4 Intensity

For solicited reactions, missing intensities will be handled as described in [Section 4.4.1.1.1](#). For unsolicited AEs, missing intensities will remain missing and will not be imputed.

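### A solicited reaction the investigator confirmed but that has no daily records falls out of the primary safety rates, because the SAP has no rule for it

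*SAP*

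**What the plan says.** Solicited injection site and systemic reactions are primary endpoints (Protocol 9.1.1.2), and all analyses are descriptive (SAP 5.1.1.2).

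SAP 4.4.1.1.1 derives daily intensity in two steps.

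- Step 1 covers every reaction other than fever, where the investigator has answered that it was absent "and with all daily records missing then all daily intensities will be derived as None".
- Step 2 relies on the daily data alone: "For non-measurable solicited reactions, daily intensities will correspond to daily records reported in the clinical database". Measured reactions are converted from their daily measurements.

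Maximum intensity is the highest daily intensity over the period (4.4.1.1.2), and presence is read from it (4.4.1.1.3). A missing maximum gives "Missing: Missing presence", and "those without a non-missing presence will not be included in the analysis of the endpoint".

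The section on missing intensities adds nothing further: "For solicited reactions, missing intensities will be handled as described in" 4.4.1.1.1 (SAP 5.3.1.4). SAP 5.3.1 and Protocol 12.3.1 provide for no replacement of missing safety data, in general terms and outright respectively. No step mentions an investigator answer of Yes when every daily record is missing.

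**The concern.** The investigator's answer is used when it is No and has no effect when it is Yes. A subject whose headache the site has confirmed, but whose daily grades were never recorded, does not appear as a headache case. The subject disappears from that line of the table.

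The trial tests no hypotheses, so the reported percentages are the result. A gap that can only remove reactors from a primary safety table deserves closing even if it is seldom used.

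Elsewhere the SAP leans the cautious way. Missing causality is taken as related (5.3.1.2), and unsolicited events with missing onset stay in the analysis (4.4.1.2.3). For discontinuations, unsolicited events with missing grade are counted, but solicited ones only from Grade 1 upward (4.4.1.5.6).

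Summaries that pool several reactions or several injections carry a second risk. SAP 4.4.1.1.3 includes a subject with at least one non-missing presence. A subject with headache Yes and no records, but No for the other items or None after later injections, may stay in the denominator as a non-reactor.

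**Working it through.** **The plan's own figure.** The only design figure is a 95% chance of seeing an event with 3% true incidence among 100 vaccine subjects (SAP 5.5). It reproduces: 1 − 0.97^100 = 95.2%. It does not depend on the rule discussed here.

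**Following one subject through the SAP.** Investigator answer Yes for headache, all daily records missing:

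1. Step 1 does not apply, because the answer is not No.
2. Step 2 has no daily records to use, so every daily intensity is Missing.
3. Maximum intensity is Missing (4.4.1.1.2), and so is presence (4.4.1.1.3).
4. The subject is left out of the headache analysis.

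The SAP does not state this outcome in a sentence; it is what the steps produce.

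**Direction, single reaction.** Let N be the subjects who should be assessed, a the reactors with records, and y the subjects with Yes and no records.

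- Reported rate: a/(N−y)
- Rate with the confirmed reactions counted: (a+y)/N
- Shortfall: (a+y)/N − a/(N−y) = y(N−a−y)/[N(N−y)]

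The shortfall is never negative. It is zero only if y = 0 or if everyone reacted.

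This holds for pain, headache, malaise, myalgia and asthenia, where any Yes is at least Grade 1 on the scales in Protocol Tables 9.1 and 9.2. For erythema and swelling the direction is not fixed: an unmeasured Yes may have been under 25 mm, which SAP 4.4.1.1.2 says is analysed as no reaction.

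**Illustrative size.** Neither document gives y, so y = 1, 2 and 5 are assumptions. N = 100 is the planned vaccine group. The numbers of true reactors are rounded from the adult rates after any injection in Protocol 1.3.2 (asthenia 28.3%, pain 45.2%, headache 51.4%).

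| True reactors in 100 | y = 1 | y = 2 | y = 5 |
|---|---|---|---|
| 28 (asthenia) | 27/99 = 27.3%, −0.7 | 26/98 = 26.5%, −1.5 | 23/95 = 24.2%, −3.8 |
| 45 (pain) | 44/99 = 44.4%, −0.6 | 43/98 = 43.9%, −1.1 | 40/95 = 42.1%, −2.9 |
| 51 (headache) | 50/99 = 50.5%, −0.5 | 49/98 = 50.0%, −1.0 | 46/95 = 48.4%, −2.6 |

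These rates are after any injection, so a subject is lost in this way only if no injection left a graded reaction.

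**Composite.** Take 73 true reactors in 100 (any solicited reaction, 73.2%), and let y of them have only ungraded reactions.

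- If they are dropped: 72/99 = 72.7%, 71/98 = 72.4% and 68/95 = 71.6%.
- If missing components are ignored and they count as None: 72%, 71% and 68%, a shortfall of exactly y points.

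The SAP does not say which applies.

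**The case against.** The strongest reply is that step 1 does not deal with lost diaries. Protocol Tables 9.1 and 9.2 define Grades 1 to 3 only, and their footnotes have subjects enter a grade or a size. A subject without headache has nothing to enter, so No with blank days most naturally describes an ordinary non-reactor. Temperature is taken every day regardless, which explains why fever is excepted. Step 1 would therefore be needed even with perfect diaries.

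That reply stands, and it rules out several readings that may tempt a reader:

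- *That the same lost diary is kept for No and deleted for Yes.* Blank days are normal after No and anomalous after Yes. Applying an equal missing fraction to both answers has no basis in the documents.
- *That both answers should be left Missing.* This would remove ordinary non-reactors and push the rates upward.
- *That the vaccine is made to look closer to placebo.* For a given y the shortfall depends on the number of non-reactors. If a share m of reactors lacks records, it is mp(1−p)/(1−mp). At m = 10% that is 2.6 points at p = 51.4% but 2.1 at 73.2%, so it does not grow steadily with the reaction rate. Protocol 1.3.2 gives no placebo rates for solicited reactions.

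The reply also notes that Yes with no daily record is an inconsistency the sites are meant to resolve: interviews to clarify incomplete diaries (Protocol 11.1), consistency checks and queries (11.2), and verbal clarification transferred to the case report book (13.2). This should make the case rare. It does not say what the analysis does with a case that remains.

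**Conclusion.** The gap is real and narrow. The SAP has no rule for an investigator Yes without daily records, and its steps turn such a subject into Missing. For the five subjectively graded reactions, any resulting error understates the rate.

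The size cannot be estimated from the documents. It is zero if no such subject remains after data cleaning, and the site procedures should keep it small. In a group of 100 with about 45 true reactors, each such subject costs a little over half a point for a single reaction, and one full point in a composite that treats the subject as a non-reactor.

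A reader might infer that the primary reactogenicity rates are biased downward by a material amount. The documents do not support that: they give no number of such cases, and step 1 is legitimate and should stay. The conclusion rests on reading steps 1 and 2 as the complete derivation, which SAP 5.3.1.4 confirms by referring back to them.

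**What to change.** Keep step 1. Add to SAP 4.4.1.1.3:

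- For pain, headache, malaise, myalgia and asthenia, an investigator answer of Yes with all daily records missing counts as present with maximum intensity Missing. The subject enters numerator and denominator, and counts as present in composite and any-injection summaries.
- For erythema, swelling and fever, such a case stays Missing, because an unmeasured Yes cannot be placed on the intensity scale.
- A composite is Missing, not None, when the only possible reaction in it is one of these ungraded Yes answers.
- The number of subjects with Yes and no daily records is reported by reaction, group and injection, so that a reader can bound what remains for erythema, swelling and fever.

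The cost is a short SAP addition and a small programming change, best made before unblinding. The intensity tables gain a missing row, and the rates may become slightly less favourable.
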